A newer proposed treatment for CECS is the intramuscular administration of botulinum toxin A (BoNT-A) into the muscles of the involved compartment(s). BoNT-A is FDA approved for intramuscular, intradetrusor, or intradermal use for muscle spasticity, migraine headaches, detrusor instability and severe forehead lines, lateral canthal lines, and glabellar lines in adults. A 2013 case series studying botulinum toxin injections for CECS demonstrated normalized intramuscular pressure up to nine months post-injection in 87.5% (14/16) of patients, and exertional pain was completely eliminated in 94% (15/16) of patients. Eleven patients experienced reduced muscle strength that was without functional consequences and transient resolving within 3 months. Only 1 of the 16 patients complained of new posterior leg pain that did not appear to be related to BoNT-A injections. There were no other adverse effects reported.¹ An additional 2016 case report showed effective pain and paresthesia relief from CECS after 1 set of injections for a recreational female athlete. In this report, the patient's symptoms resolved within 1 week. More importantly, she was able to return to full recreational activity within 4 weeks, with no return of symptoms throughout the 14 months of follow up without any weakness or adverse effect.²

Military sports medicine clinics at Fort Belvoir Community Hospital (FBCH) and the Uniformed Services University (USU) as well as the Department of Physical Medicine & Rehabilitation at Walter Reed National Military Medical Center WRNMMC) currently utilize BoNT-A (trade names BOTOX® or Xeomin®) injections for the non-surgical treatment of CECS. All of our performance sites currently offer BoNT-A (trade names BOTOX® or Xeomin®) injections as standard of care non-surgical treatment options for CECS.

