Chronic exertional compartment syndrome (CECS) may occur in the four compartments of the lower leg: anterior, lateral, superficial posterior, and deep posterior. CECS typically occurs in the anterior and/or lateral compartments and is commonly seen within the military and has been shown to result in both significant warfighter disability and degradation of the unit mission. Active duty military members represent a population with a significantly higher risk of CECS. Military members also face requirements for exercise training and fitness that are jeopardized by a condition that limits aerobic exercise and physical activity. Fasciotomy, the current standard definitive treatment, has significant limitations in terms of effectiveness and direct and indirect costs. Pooled data shows that 28-59% of military members with CECS who underwent fasciotomy were unable to return to full duty and approximately 20% ultimately required medical separation from the military.¹ Not included in these statistics was the loss of member productivity during appointments, procedures, and recovery time.

Given the significant impact of CECS on the military mission, there is strong interest and motivation to investigate less invasive and less costly alternatives to fasciotomy. Within the National Capital Region, military sports medicine physicians have been utilizing both Supervised Gait Retraining (SGR) and botulinumtoxin A (BoNT-A) injections for years. While results have been promising for both options, there is insufficient high-quality data to create treatment guidelines and protocols for other providers in the military who treat these patients.

Based on a retrospective review of 29 patients from Fort Belvoir Community Hospital who received BoNT-A injections for CECS, approximately two-thirds of these patients were able to return to their desired activity level. In addition, among 11 patients who eventually underwent both BoNT-A injections and fasciotomy, only 2 patients would recommend fasciotomy as the first intervention over BoNT-A. Additionally, 69% of the patients in this review expressed satisfaction with BoNT-A injections. Aside from self-limited weakness with ankle dorsiflexion, there were no significant adverse effects.² The next logical step is to study the effect of BoNT-A injections in a randomized, prospective, single-blinded, placebo- controlled fashion.

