The potential side effects of Botulinum toxin A injections include: rare minor side effects of bleeding, pain, soreness, infection, transient general muscle weakness and muscular atrophy, flu-like symptoms, and even rarer transient breathing and swallowing difficulties which has the potential to cause death if not appropriately treated.

The potential side effects of saline injections include: pain, soreness, bleeding, and infection which are all very rare.

The potential side effects of IMCP needle insertion for intramuscular compartment pressure testing include: pain which is minimized with local anesthesia, soreness, minor local bleeding, and the rare incidence of infection.

The potential risks for balance screening, physical objective measurements, physical performance based testing, gait retraining, standard gait analysis, self-paced treadmill test, and lower strengthening and stretching exercises include: physical discomfort (increased pain and reduced activity level), soreness, possible chronic or acute musculoskeletal injury, overuse or a fall.

Any time information is collected for a study, there is a small risk of breach of confidentiality.

14.2

Measures to Minimize Risks of Harm (Precautions, safeguards):

For each research procedure or intervention, describe all measures to minimize and/or eliminate risk of harms to subjects and study personnel

All available precautions will be taken to minimize the above-mentioned risks. Standard clinic protocols will be followed to reduce the risks of infections and related complications.

To minimize the risk to participants, once they receive their injection, a waiting period of at least 15 minutes will occur at the clinic. This waiting period is to observe for any side effects that may occur due to the injection. The participant will also be given an after care injection handout. In order to safeguard participants, providers will use ultrasound guidance to identify the locations of the anterior and lateral compartments of the lower leg. Expected soreness may occur from the study injection procedures which may impact the start of physical therapy visits to 2 weeks post injection. Providers will be trained on all study procedures. All of this will provide consistent delivery of treatment to the targeted areas and minimize risk to the participant.

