All Serious Adverse Events (SAEs) that are unexpected and related, or possibly related, to study participation will be reported to the IRB and the Research Monitor via telephone or email within 24 hours of discovery and a complete written report via eIRB will follow within 5 business days.

Unanticipated Problems Involving Risks to Subjects or Others (UPIRTSOs) will be reported to the IRB and the Research Monitor via telephone or email within 24 hours of discovery and a complete written report via eIRB will follow within 5 business days.

Unexpected (but not serious) adverse events occurring in subjects enrolled at WRNMMC which, in the opinion of the PI, are related or possibly related to study participation AND places subjects or others at a greater risk of harm that was previously known or recognized in the protocol will be reported to the IRB and Research monitor via telephone or email within 24 hours of discovery and a complete written report via eIRB will follow within 5 business days.

Expected adverse events and AEs/SAEs that are not related or not possibly related to study participation will be tracked by the local study team using an Adverse Event Tracking Log and reported to the IRB at the time of continuing review or, if applicable, at study closure. Continuing Review (CR) Progress Reports are generally performed on a 12-month cycle. More frequent Progress Reports may be required at the discretion of the IRB.

Because this is a multi-center study, a summary of adverse events study-wide will be included with the CR.

Protocol Deviations:

All protocol deviations, both major and minor, will be reported to the Principal Investigator. The Principal Investigator will review all protocol deviations.

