Route of administration:	injection
Will the investigational pharmacy be dispensing?	No
If the source is not a FDA licensed facility, provide details regarding the purity, quality, stability and sterility of the investigational drug/biologic:	N/A - the source is an FDA licensed facility
Identify who will be preparing the investigational drug /biologic for administration and describe in detail how it will be prepared:	The BoNT-A will be prepared by a trained physician or nurse. Four syringes using 25 units of BoNT-A and 1 mL of normal saline will be prepared per limb.
Indication(s) under Investigation:	BoNT-A (trade name BOTOX, generic name onabotulinumtoxinA) is currently FDA approved for injection into extremity musculature for other medical conditions (i. e. muscular hypertrophy/spasticity). We are investigating its usage for chronic exertional compartment syndrome.
Where will the drug be stored	Within a locked cabinet in a Dept. of Physical Medicine & Rehabilitation procedure room
Drug Storage Restrictions (including temperature, etc.):	Unopened vials of BoNT-A (trade name BOTOX, generic name (onabotulinumtoxinA) will be stored in a refrigerator set for 2°C to 8°C or 36°F to 46°F.
Administration Instructions:	Standard aseptic technique will be followed. Insertion of the correct compartment will be accomplished using ultrasound guidance. The anterior and lateral compartment will be separated into thirds measuring from the tibial plateau to the head of the calcaneus. Injections will be given at approximately 1/3 the distance from the tibial plateau for the proximal injection and 2/3 the distance from the tibial plateau for the distal injection. Injections will only be given to compartments that have elevated pressures. If the lateral compartment is affected, the peroneus longus and brevis muscles will receive 25 units proximally and 25 units distally, for a total of 50 units, of BoNT-A. If the anterior compartment is affected, a total of 50 units of BoNT-A will be given: 25 units at the proximal region and 25 units at the distal region.
Possible Untoward Effects, Their Symptoms & Treatment:	The potential side effects for BoNT-A (trade name BOTOX, generic name onabotulinumtoxinA) include: rare minor side effects of bleeding, pain, infection, transient general muscle weakness and muscular atrophy, flu-like symptoms, and even rarer transient breathing and swallowing difficulties which has the potential to cause death if not appropriately treated.

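### Sections 14.1 and 18.2 place muscle weakness after BoNT-A among rare side effects, while section 9.2 reports reduced strength in 11 of 16 treated patients; the passages need reconciling

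*Combined protocol and SAP*

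**What the plan says.** Section 14.1 (Risks of Harm) gives the side effects of BoNT-A as "rare minor side effects of bleeding, pain, soreness, infection, transient general muscle weakness and muscular atrophy", followed by flu-like symptoms and, as rarer still, difficulty in breathing and swallowing. The Botox and Xeomin tables in section 18.2 both say "rare minor side effects of bleeding, pain, infection, transient general muscle weakness and muscular atrophy". None of the three places gives a number.

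The background reads differently. On the 2013 BoNT-A case series, section 9.2 states: "Eleven patients experienced reduced muscle strength that was without functional consequences and transient resolving within 3 months". On the retrospective review of 29 patients at one of the military hospitals, section 9.6 states: "Aside from self-limited weakness with ankle dorsiflexion, there were no significant adverse effects". That review gives no count for weakness.

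There is a smaller mismatch on soreness. Section 14.1 describes all the listed effects of saline injection, soreness among them, as very rare. Section 14.2 treats soreness after study injections as something to expect, and as able to affect when physical therapy starts.

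**The concern.** Section 14.1 is where the protocol states research risks to the IRB. It singles out the injection as the one study activity that is not regularly performed in standard care for this condition. The frequency given there for the injection's most visible effect therefore matters.

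A reader of section 14.1 alone would expect weakness to be unusual. A reader of section 9.2 would expect it in most injected patients. Participants go on to treadmill tests and gait retraining, for which section 14.1 itself lists a fall among the risks. They should be able to learn that temporary weakness is likely, and also that the series found it had no effect on function.

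The form's prompt for section 16.1 asks for the likelihood of each expected event, and the section gives none. Section 15.1 aims to detect early any increase in the risk of a known adverse event. For weakness, the only frequency in the safety sections against which an increase could be judged is the word rare.

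**Working it through.** **1. Denominator.** Section 9.2 gives two results for the series as percentages with counts: 14/16 = 87.5% and 15/16 = 93.75%, stated as 94%. Both reproduce. The same paragraph also says "Only 1 of the 16 patients complained of new posterior leg pain". The eleven patients with reduced strength are therefore eleven of 16.

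**2. Observed rate.** 11/16 = 0.6875, or 69%. The exact (Clopper-Pearson) 95% interval with x = 11 and n = 16 is:
- lower limit: 2.5% quantile of Beta(x, n − x + 1) = Beta(11, 6) = 0.413
- upper limit: 97.5% quantile of Beta(x + 1, n − x) = Beta(12, 5) = 0.890

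**3. Does rare cover weakness?** The sentence in section 14.1 runs "rare minor side effects of bleeding, pain, soreness, infection, transient general muscle weakness and muscular atrophy, flu-like symptoms, and even rarer transient breathing". The comparative near the end makes sense only if everything before it, including weakness, is being called rare.

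**4. Could a rare effect give 11 of 16 by chance?** The protocol does not define rare, so a range is assumed. P(X ≥ 11) is the sum over k = 11 to 16 of C(16, k) p^k (1 − p)^(16 − k):

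| Assumed true rate p | P(11 or more of 16) |
|---|---|
| 1% | 4 × 10⁻¹⁹ |
| 5% | 1.7 × 10⁻¹¹ |
| 10% | 2.7 × 10⁻⁸ |
| 20% | 3.3 × 10⁻⁵ |

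The small size of the series does not explain the discrepancy.

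**5. Lower bound from both sources.** Suppose none of the 29 review patients had weakness. Section 9.6 says otherwise, so this is deliberately too favourable. The pooled rate is then (11 + 0)/(16 + 29) = 11/45 = 24% (exact 95% CI 13% to 40%).

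**6. Scale in this trial.** Section 11.2 plans a final sample of 120 per group. Groups 3 and 4 receive BoNT-A, so 2 × 120 = 240.
- At the observed rate: 240 × 0.6875 = 165
- At the interval limits: 240 × 0.4134 = 99 and 240 × 0.8898 = 214
- At assumed rates of 1% to 10%: 2 to 24

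**7. The word general.** There are two readings:
- It covers weakness of any kind. The stated frequency then conflicts with section 9.2.
- It means systemic weakness. The frequency may then be correct, but sections 14.1 and 18.2 do not mention weakness of the injected muscles, although the prompt for 14.1 asks for all research-related risks.

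Section 14.1 and both 18.2 tables need correction on either reading.

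**The case against.** **The passages may describe different effects.** Sections 14.1 and 18.2 speak of general weakness, section 9.2 of reduced strength, and section 9.6 of ankle dorsiflexion. Section 9.2 does not name the muscle. Taking it as local weakness is an inference, though a natural one, since the toxin is injected into the muscles of the affected compartments and section 9.6 names ankle dorsiflexion. This stands as a reason not to claim a flat contradiction. It turns the defect into an omission and does not remove it.

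**The weakness was mild.** Section 9.2 says it was transient and without functional consequences. This stands and belongs in any disclosure. It bears on severity, not on frequency.

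**The evidence is thin.** There is one uncontrolled series of 16, and the protocol does not give its dose or how strength was measured. The larger review has no count. So 69% is context, not a rate to build a threshold on.

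**The IRB already has the facts.** Sections 9.2 and 9.6 are in the same protocol, and section 10.1 has ankle strength measured at 8 weeks and at 3, 6 and 12 months. This lowers the urgency, but the stated risk is still not supported by the protocol's own figures.

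**Event reporting.** A reader might infer that the wording would set off many expedited reports under section 16.1. The documents do not support this. The clause "places subjects or others at a greater risk of harm that was previously known or recognized in the protocol" applies only to events that are unexpected, not serious, related or possibly related, and in participants enrolled at one named site. Section 16.1 has no rate-based trigger. Weakness that is listed counts as expected and goes to the tracking log and continuing review, and all adverse events reach the principal investigator and the research medical monitor. What remains is that section 16.1 gives no expected frequencies. Under the systemic reading, it is also unclear whether local weakness counts as expected.

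**Consent.** A reader might also infer that participants are being told the wrong rate. That cannot be established: the consent form and the after-care handout are not among the documents, and section 13.4 says only that the form will describe the risks.

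**Conclusion.** The point holds as an inconsistency in the stated risk and should be fixed. On one reading, sections 14.1 and 18.2 give a frequency for weakness that section 9.2 contradicts (69%, 95% CI 41% to 89%). On the other, they omit the commonest unwanted effect in the protocol's own evidence. No passage supports rare for weakness of the injected muscles.

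The projection of about 165 of 240 participants (99 to 214) assumes that the 16-patient series applies to this trial's injections and population. It should not be scaled to all 310 (2 × 155) who could be enrolled to the BoNT-A groups. Section 11.5 says the enrolment figure of 620 allows for screen failures as well as attrition, so 310 is a ceiling. Participants who cross over to BoNT-A after month 3 (section 10.1) would add to the number exposed, by an amount the documents do not let one estimate.

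The hypotheses, power calculation and planned analysis are not affected. The soreness mismatch is minor and can be settled in the same edit.

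**What to change.** Reconcile section 14.1 and both product tables in section 18.2 with sections 9.2 and 9.6:

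- List weakness of the injected muscles, including ankle dorsiflexion, separately from generalised weakness. Stop calling the local effect rare.
- Cite 11 of 16 patients in the one series, with its wide interval (41% to 89%), and say that the weakness resolved within 3 months and had no functional consequences. Mention that the 29-patient review also saw it, without a count.
- In section 16.1, name local weakness as an expected event. Give the approximate frequency as context only, not as a reporting threshold.
- Make the soreness statements in sections 14.1 and 14.2 agree.
- Check the consent form and the after-care handout (Appendix O) for the same wording, and change them only if it is there.

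The cost is a wording amendment to sections 14.1, 14.2, 16.1 and 18.2, and possibly to two participant documents. The design, treatment and analysis do not change. One drawback is that participants told more about weakness may be more alert to it as a clue to their injection during the three blinded months.

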17.1 Does the study involve the use of any unique non-medical devices/equipment?

☐ Yes ☒ No

18.0

FDA-Regulated Products

18.1 Will any drugs, dietary supplements, biologics, or devices be utilized in this study?

- ☒ Drugs
- ☐ Dietary Supplements
- ☐ Biologics
- ☐ Devices
- ☐ N/A

18.2 Drugs, Dietary Supplements and Biologics/Vaccines details:

- ☐ Are drug(s) in this research being used in accordance to the approved labeling?
- ☒ Are drug(s) in this research being used in a manner other than its approved labeling?

Enter Dietary Supplements and Biologics/Vaccines in the Drug Information table. Complete all relevant fields in the table ("Protocol Drug Details" screen). If the question is not relevant, leave the question blank and/or do not change the default selection.

View Details	Drug Name	FDA Approved	A new drug or a new use of an already approved drug:	IND Number																								
	Trade Drug Name: Botox Generic Drug Name: Investigational Drug Name:	Yes	Yes																									

 
 Trade Drug Name:	Botox	
 
 Generic Drug Name:		
 
 Investigational Drug Name:		
 
 Identify the name of the manufacturer or source of investigational drug/biologic:	Allergan	
 
 Is the drug supplied at no cost?	Yes	
 
 Is the Drug FDA Approved:	Yes	
 
 Is this a new drug or a new use of an already approved drug	Yes	
 
 Is an IND necessary	No	
 
 IND Number		
 
 Who holds the IND:	N/A	
 
 IND details:	N/A - please see section below for exemption rationale.	
 
 If FDA Approved and an IND is not required, Please provide a rationale for exemption:	 BotulinumtoxinA injections are already currently used in the sports medicine clinics at Fort Belvoir Community Hospital (FBCH) and the Uniformed Services University (USU) as well as in the Dept. of Physical Medicine & Rehabilitation (PM&R) at Walter Reed National Military Medical Center (WRNMMC) for the non-surgical treatment of CECS. Additionally, our use of BoNT-A in this study does not require an IND because it meets all of the required exemption criteria outlined by the FDA: 1) The drug we propose to use is currently lawfully marketed in the United States. 2) This study/investigation is not intended to be reported to the FDA as a well-controlled study. This study is also not intended to support neither a new indication of this drug nor a change to the current labeling of this drug. 3) This study does not intend to support a significant change in advertising for the drug. 4) Although this drug is not currently explicitly approved for the treatment of CECS, it is 	
 
					Trade Drug Name:	Botox	Generic Drug Name:		Investigational Drug Name:		Identify the name of the manufacturer or source of investigational drug/biologic:	Allergan	Is the drug supplied at no cost?	Yes	Is the Drug FDA Approved:	Yes	Is this a new drug or a new use of an already approved drug	Yes	Is an IND necessary	No	IND Number		Who holds the IND:	N/A	IND details:	N/A - please see section below for exemption rationale.	If FDA Approved and an IND is not required, Please provide a rationale for exemption:	BotulinumtoxinA injections are already currently used in the sports medicine clinics at Fort Belvoir Community Hospital (FBCH) and the Uniformed Services University (USU) as well as in the Dept. of Physical Medicine & Rehabilitation (PM&R) at Walter Reed National Military Medical Center (WRNMMC) for the non-surgical treatment of CECS. Additionally, our use of BoNT-A in this study does not require an IND because it meets all of the required exemption criteria outlined by the FDA: 1) The drug we propose to use is currently lawfully marketed in the United States. 2) This study/investigation is not intended to be reported to the FDA as a well-controlled study. This study is also not intended to support neither a new indication of this drug nor a change to the current labeling of this drug. 3) This study does not intend to support a significant change in advertising for the drug. 4) Although this drug is not currently explicitly approved for the treatment of CECS, it is
Trade Drug Name:	Botox																											
Generic Drug Name:																												
Investigational Drug Name:																												
Identify the name of the manufacturer or source of investigational drug/biologic:	Allergan																											
Is the drug supplied at no cost?	Yes																											
Is the Drug FDA Approved:	Yes																											
Is this a new drug or a new use of an already approved drug	Yes																											
Is an IND necessary	No																											
IND Number																												
Who holds the IND:	N/A																											
IND details:	N/A - please see section below for exemption rationale.																											
If FDA Approved and an IND is not required, Please provide a rationale for exemption:	BotulinumtoxinA injections are already currently used in the sports medicine clinics at Fort Belvoir Community Hospital (FBCH) and the Uniformed Services University (USU) as well as in the Dept. of Physical Medicine & Rehabilitation (PM&R) at Walter Reed National Military Medical Center (WRNMMC) for the non-surgical treatment of CECS. Additionally, our use of BoNT-A in this study does not require an IND because it meets all of the required exemption criteria outlined by the FDA: 1) The drug we propose to use is currently lawfully marketed in the United States. 2) This study/investigation is not intended to be reported to the FDA as a well-controlled study. This study is also not intended to support neither a new indication of this drug nor a change to the current labeling of this drug. 3) This study does not intend to support a significant change in advertising for the drug. 4) Although this drug is not currently explicitly approved for the treatment of CECS, it is																											

	currently FDA approved for injection into extremity musculature for other medical conditions. We will be using this drug following a similar dosing guideline, using a similar route of administration, and in a population that it is already FDA approved for. Our intended procedures do not significantly increase the risks associated with the use of this drug. 5) This study will be conducted in compliance with the requirements for review by our IRB board. 6) This study is not intended to promote or commercialize this drug product.
Are you currently using this IND in another research project?	No
If yes, list the IRB Number(s):	N/A
Dose Range:	50-100 units per limb
Frequency:	one time
Route of administration:	injection
Will the investigational pharmacy be dispensing?	No
If the source is not a FDA licensed facility, provide details regarding the purity, quality, stability and sterility of the investigational drug/biologic:	N/A - the source is an FDA licensed facility
Identify who will be preparing the investigational drug /biologic for administration and describe in detail how it will be prepared:	The BoNT-A will be prepared by a trained physician or nurse. Four syringes using 25 units of BoNT-A and 1 mL of normal saline will be prepared per limb.
Indication(s) under Investigation:	BoNT-A (trade name BOTOX, generic name onabotulinumtoxinA) is currently FDA approved for injection into extremity musculature for other medical conditions (i. e. muscular hypertrophy/spasticity). We are investigating its usage for chronic exertional compartment syndrome.
Where will the drug be stored	Within a locked cabinet in a Dept. of Physical Medicine & Rehabilitation procedure room
Drug Storage Restrictions (including temperature, etc.):	Unopened vials of BoNT-A (trade name BOTOX, generic name (onabotulinumtoxinA) will be stored in a refrigerator set for 2°C to 8°C or 36°F to 46°F.
Administration Instructions:	Standard aseptic technique will be followed. Insertion of the correct compartment will be accomplished using ultrasound guidance. The anterior and lateral compartment will be separated into thirds measuring from the tibial plateau to the head of the calcaneus. Injections will be given at approximately 1/3 the distance from the tibial plateau for the proximal injection and 2/3 the distance from the tibial plateau for the distal injection. Injections will only be given to compartments that have elevated pressures. If the lateral compartment is affected, the peroneus longus and brevis muscles will receive 25 units proximally and 25 units distally, for a total of 50 units, of BoNT-A. If the anterior compartment is affected, a total of 50 units of BoNT-A will be given: 25 units at the proximal region and 25 units at the distal region.
Possible Untoward Effects, Their Symptoms & Treatment:	The potential side effects for BoNT-A (trade name BOTOX, generic name onabotulinumtoxinA) include: rare minor side effects of bleeding, pain, infection, transient general muscle weakness and muscular atrophy, flu-like symptoms, and even rarer transient breathing and swallowing difficulties which has the potential to cause death if not appropriately treated.

Potential or Actual Antidotes for Excessive or Adverse Drug Effect:	Potential excessive BoNT-A (trade name BOTOX, generic name onobotulinumtoxinA) drug effect may produce neuromuscular weakness with a range of symptoms and should be medically treated immediately and may require hospitalization. In the event of an overdose, an antitoxin is available through contact with the local and state health departments to the CDC. The antitoxin will not reverse any effects that have occurred prior to the antitoxin administration.
Contraindications and Interactions, If Known:	Individuals who have known hypersensitivity to BoNT-A (trade name BOTOX, generic name onobotulinumtoxinA) or its ingredients/components and individuals that have a presence of infection at the site of injection.
Investigators Authorized to Prescribe:	[name]

	Trade Drug Name: Xeomin Generic Drug Name: Investigational Drug Name:	Yes	Yes	
--------------------------	--	-----	-----	--

Trade Drug Name:	Xeomin
Generic Drug Name:	
Investigational Drug Name:	
Identify the name of the manufacturer or source of investigational drug/biologic:	Merz Pharmaceuticals
Is the drug supplied at no cost?	Yes
Is the Drug FDA Approved:	Yes
Is this a new drug or a new use of an already approved drug	Yes
Is an IND necessary	No
IND Number	
Who holds the IND:	N/A
IND details:	N/A - please see section below for exemption rationale.
If FDA Approved and an IND is not required, Please provide a rationale for exemption:	
botulinumtoxinA injections are already currently used in the sports medicine clinics at Fort Belvoir Community Hospital (FBCH) and the Uniformed Services University (USU) as well as in the Dept. of Physical Medicine & Rehabilitation (PM&R) at Walter Reed National Military Medical Center (WRNMMC) for the non-surgical treatment of CECS. Additionally, our use of BoNT-A in this study does not require an IND because it meets all of the required exemption criteria outlined by the FDA: 1) The drug we propose to use is currently lawfully marketed in the United States. 2) This study/investigation is not intended to be reported to the FDA as a well-controlled study. This study is also not intended to support neither a new indication of this drug nor a change to the current labeling of this drug. 3) This study does not intend to support a significant change in advertising for the drug. 4) Although this drug is not currently explicitly approved for the treatment of CECS, it is currently FDA approved for injection into extremity musculature for other medical conditions. We will be using this drug following a similar dosing guideline, using a similar route of administration, and in a population that it is already FDA approved for. Our intended procedures do not significantly increase the risks associated with the use of

	this drug. 5) This study will be conducted in compliance with the requirements for review by our IRB board. 6) This study is not intended to promote or commercialize this drug product.
Are you currently using this IND in another research project?	No
If yes, list the IRB Number(s):	N/A
Dose Range:	50-100 units per limb
Frequency:	One time
Route of administration:	Injection
Will the investigational pharmacy be dispensing?	No
If the source is not a FDA licensed facility, provide details regarding the purity, quality, stability and sterility of the investigational drug/biologic:	N/A - the source is an FDA licensed facility
Identify who will be preparing the investigational drug /biologic for administration and describe in detail how it will be prepared:	The BoNT-A will be prepared by a trained physician or nurse. Four syringes using 25 units of BoNT-A and 1 mL of normal saline will be prepared per limb.
Indication(s) under Investigation:	BoNT-A (trade name Xeomin, generic name incobotulinumtoxinA) is currently FDA approved for injection into extremity musculature for other medical conditions (i.e. muscular hypertrophy/spasticity). We are investigating its usage for chronic exertional compartment syndrome.
Where will the drug be stored	Within a locked cabinet in a Dept. of Physical Medicine & Rehabilitation procedure room
Drug Storage Restrictions (including temperature, etc.):	Unopened vials of BoNT-A (trade name Xeomin, generic name incobotulinumtoxinA) will be stored at room temperature 20°C to 25°C (68°F to 77°F).
Administration Instructions:	Standard aseptic technique will be followed. Insertion of the correct compartment will be accomplished using ultrasound guidance. The anterior and lateral compartment will be separated into thirds measuring from the tibial plateau to the head of the calcaneus. Injections will be given at approximately 1/3 the distance from the tibial plateau for the proximal injection and 2/3 the distance from the tibial plateau for the distal injection. Injections will only be given to compartments that have elevated pressures. If the lateral compartment is affected, the peroneus longus and brevis muscles will receive 25 units proximally and 25 units distally, for a total of 50 units, of BoNT-A. If the anterior compartment is affected, a total of 50 units of BoNT-A will be given: 25 units at the proximal region and 25 units at the distal region.
Possible Untoward Effects, Their Symptoms & Treatment:	The potential side effects for BoNT-A (trade name Xeomin, generic name incobotulinumtoxinA) include: rare minor side effects of bleeding, pain, infection, transient general muscle weakness and muscular atrophy, flu-like symptoms, and even rarer transient breathing and swallowing difficulties which has the potential to cause death if not appropriately treated.
Potential or Actual Antidotes for Excessive or Adverse Drug	Potential excessive BoNT-A (trade name Xeomin, generic name incobotulinumtoxinA) drug effect may produce neuromuscular weakness with a range of symptoms and should be medically treated immediately and may require hospitalization. In the event of an overdose, an antitoxin is

Effect:	available through contact with the local and state health departments to the CDC. The antitoxin will not reverse any effects that have occurred prior to the antitoxin administration.
Contraindications and Interactions, If Known:	Individuals who have known hypersensitivity to BoNT-A (trade name Xeomin, generic name incobotulinumtoxinA) or its ingredients/components and individuals that have a presence of infection at the site of injection.
Investigators Authorized to Prescribe:	[name]

18.4 Reporting Requirements for FDA-regulated research under IND and IDE:

Describe the process for complying with FDA regulatory requirements for adverse event reporting and adverse device effects reporting to the sponsor

N/A

BotulinumtoxinA injections are already currently used in the sports medicine clinics at Fort Belvoir Community Hospital (FBCH) and the Uniformed Services University (USU) as well as in the Dept. of Physical Medicine & Rehabilitation (PM&R) at Walter Reed National Military Medical Center (WRNMMC) for the non-surgical treatment of CECS.

Additionally, our use of BoNT-A in this study does not require an IND because it meets all of the required exemption criteria outlined by the FDA:

1. The drug we propose to use is currently lawfully marketed in the United States.
2. This study/investigation is not intended to be reported to the FDA as a well-controlled study. This study is also not intended to support neither a new indication of this drug nor a change to the current labeling of this drug.
3. This study does not intend to support a significant change in advertising for the drug.
4. Although this drug is not currently explicitly approved for the treatment of CECS, it is currently FDA approved for injection into extremity musculature for other medical conditions. We will be using this drug following a similar dosing guideline, using a similar route of administration, and in a population that it is already FDA approved for. Our intended procedures do not significantly increase the risks associated with the use of this drug.
5. This study will be conducted in compliance with the requirements for review by our IRB board.
6. This study is not intended to promote or commercialize this drug product.

18.5 Sponsor (organization/institution/company):

☐ N/A

If applicable, provide sponsor contact information:

[name], CAQSM
Walter Reed National Military Medical Center
Uniformed Services University
[contact]
[contact]

19.0

Research Registration Requirements

19.1 ClinicalTrials.gov Registration:

- ☐ Registration is not required
- ☐ Registration pending

☒ Registration complete

"NCT" number:

NCT04409600

